## CHAPTER 1 INTRODUCTION

### 1.0 INTRODUCTION

Osteoarthritis (OA) is thought to be the most prevalent chronic joint disease. The incidence of osteoarthritis is rising because of the ageing population and the epidemic of obesity. Pain and loss of function are the main clinical features that lead to treatment, including non-pharmacological, pharmacological, and surgical approaches (Bijlsma, Berenbaum, & Lafeber, 2011).

OA is a “joint degenerative disease characterized by the breakdown of articular cartilage, osteophyte formation, joint swelling, stiffness and pain. The disease progresses from an initial hypertrophy of the articular cartilage to degeneration of the cartilage and underlying bone. Osteophytes also grow throughout the affected joint” (Binder, Hirokawa & Windhorst, 2009). However, there are sometimes local signs of inflammation and it is not primarily an inflammatory disorder. Besides, it is not a pure degenerative disorder but a dynamic phenomenon since it shows features of both destruction and repair.

OA is the most common source form of arthritis globally. OA is the most prevalent chronic joint disease, which is a serious, painful and potentially life- altering joint disease mainly affecting hands, knees and hips (*Figure 1*) (Bijlsma, Berenbaum & Lafeber, 2011; Fernandes, Hagen, Bijlsma, Andreassen, Christensen, ... & Vlieland, 2013). Furthermore, OA usually affect persons aged 40 years and above and it happens gradually (National Center for Chronic Disease Prevention and Health Promotion, 2011). There are two types of OA, primary and secondary. Primary OA is related to aging, and secondary OA is usually caused by an injury that related to a person' occupation that requires kneeling or squatting for a long period of time, or diabetes, or obesity (Teitel & Zieve, 2011).

[figure not shown]

Figure 1: Osteoarthritis joints of the hand, hip and knee

“(A) Osteoarthritis is predominantly identified in the distal interphalangeal and proximal interphalangeal joints – deformations of the distal interphalangeal joints are clearly visible. (B) Plain radiograph of an osteoarthritic hip joint showing the narrowing of the joint space and clearly visible osteophytes. (C) MRI of an osteoarthritic knee with clear medial cartilage loss and osteophyte formation, with minor synovial swelling”.

## 1.1 PROBLEM STATEMENTS

The impact of osteoarthritis (OA) relates to pain and loss of joint mobility and functions. It affects individual independency and psychosocial functioning. This may lead to changes in a person’s life and the outcome of negative effects on quality of life and wellbeing (Ridder, Geenen, Kuijer & Middendorp, 2008). There are numerous studies have studied mortality among persons with OA. Nuesch, Dieppe, Reichenbach, Williams, Iff and Juni (2011) have done a study on the cause and disease specific mortality among 1163 patients aged 35 years and above with symptomatic and radiologic evidence based knee or hip OA patients. They examined that patients with OA have higher risk of death compared with general population (standardized mortality ratio 1.55, 95% confidence interval 1.41 to 1.70). Furthermore, the results revealed that OA patients with severe walking disability showed significant higher risk of death ( $p < 0.001$ ).

Australian Bureau of Statistics (2007) has reported that diseases of the musculoskeletal system are one of the underlying causes of death in less than one percent of all registered deaths in Australia. Arthritis and musculoskeletal diseases contribute standardized death rate of 4.3 per 100, 000 population in year 1998 and increases to 4.6 per 100, 000 population in year 2007, and 3.6 per 100, 000 for males and 5.3 per 100, 000 for females in year 2007, predominantly among persons aged 75 to 94 years.

According to a study on deaths from arthritis and other rheumatic conditions which done by Sacks, Helmick and Langmaid (2004) in United States, there are about 0.2 to 0.3 deaths per 100, 000 pupation due to OA within year 1979 to 1988. Besides, OA contributes approximately six percent of all arthritis- related deaths. There is an estimation of 500 deaths per year due to OA and it increases for the past ten years.

A person is defined with clinically OA if the person has the basis of symptoms and physical examination findings. A case definition of symptomatic knee or hip OA is defined where pain is present in a joint with radiographic evident based OA. In addition, radiographic defined OA is based on Kellgren or Lawrence scale or American College of Rheumatology criteria.

Lawrence, Felson, Helmick, Arnold, Choy, ... and Wolfe (2008) estimated that 13.9% of adults aged 25 and above and 33.6% (12.4 million) of those aged 65 years and above are affected by OA corresponds to 2005 United States population. Besides, the estimation of 21 million of United States adults have defined with clinical OA in year 1995 increases to 27 million for 2005.

For radiographic OA, the prevalence per 100 for hand is 7.3 (9.5 for female and 4.8 for male) (Dillon, Hirsch, Rasch & Gu, 2007); feet, 2.3 (2.7 for female and 1.5 for male) (Lawrence, Felson, Helmick, Arnold, Choy, ... & Wolfe, 2008); knee, 0.9 (1.2

for female and 0.4 for male) (Dillon, Rasch, Gu and Hirsch, 2006); and hip, 1.5 (1.4 for female and 1.4 for male) (Lawrence, Felson, Helmick, Arnold, Choy, ... & Wolfe, 2008).

Furthermore, the reported prevalence per 100 for symptomatic OA is hand contributes 8% (8.9% female; 6.7% male) corresponds to 2.9 million adults aged 60 years and above (Dillon, Hirsch, Rasch & Gu, 2007); feet contributes 2% (3.6 female; 1.6 male) corresponds to persons aged 15 to 74 years (Lawrence, Felson, Helmick, Arnold, Choy, ... & Wolfe, 2008); knee contributes 12.1% (13.6% female; 10% male) corresponds to adults aged 45 years and above (Jordan, Helmick, Renner, Luta, Dragomir, ... & Hochberg, 2007); hip contributes 4.4% (3.6% female; 5.5% male) corresponds to adults aged 55 years and above (Lawrence, Felson, Helmick, Arnold, Choy, ... & Wolfe, 2008).

OA is one of the ten most disabling diseases in developed countries. There are estimation of 9.6% of men and 18% of women aged over 60 years have symptomatic OA. 80% of those with OA will have limitations in movement, and 25% of them are unable to perform their major daily activities of life (Wittauer, Smith & Aden, 2013).

The most common region attribute by osteoarthritis in Malaysia is osteoarthritis of the knee. There are no exact figures of Malaysian population with knee osteoarthritis. However, Chia, Ng, Rabia et al. (2006) found that 21.2% of the studied population reported knee pain in the previous six months prior to the survey. This knee pain problem in Malaysia is more common in adults aged 40 years and above, and it affects Indian ethnicity the most. The Community Oriented Program for the Control of Rheumatic Diseases (COPCORD) study that done in Malaysia reported that knee was responsible for 64.8% of all complaints pertaining to the joints, and more than half those examined with knee pain had clinical evidence of osteoarthritis. Besides, there were 23% of patients over 55 years who complained in pain rate, and it increased to 39% in those over sixty five years (Veerapen, Wigley & Valkenburg, 2007).

In a systemic review done by Barlow, Wright, Sheasby, Turner and Hainsworth (2002), they emphasized on self- management which the patient is able to manage the symptoms, treatment, physical and psychosocial consequences and life style changes inherent with a chronic condition. Furthermore, self- management needs to incorporate with the "ability to monitor one's condition and to effect the cognitive, behavioral and emotional responses necessary to maintain a satisfactory quality of life". Behavioral change and new coping strategies are very important of self- management for osteoarthritis because symptoms have a great impact on many years of life (Newman, Steed & Mulligan, 2004).

Unfortunately, most of the patients with osteoarthritis of the knee are often difficult to achieve optimum self- management and thus resulting in reduced quality of life and poor psychological wellbeing. In fact, there are no self- management interventions for patients with osteoarthritis of the knee with the main focus of reducing pain and improving physical and psychological functioning which has not been previously studied in Malaysia.

The key features of cognitive behavioral intervention are the aim of increasing patients' involvement and control in their life and its effect on their lives. Cognitive behavioral intervention in this study will be delivered in a basis of group due to

groups have the advantage of participants being able to communicate or interact with each other with similar problems (Critchley, Ratcliff, Noonan, Jones & Hurley, 2007). Consequently, the group cognitive behavioral treatment in this study aims to meet the objectives of reducing pain and improving physical and psychological functioning in patients with osteoarthritis of the knee.

## **1.2 SIGNIFICANCE OF RESEARCH**

There are no risks for subjects on placebo. However, there is little risk in getting cognitive behavioral therapy. Patients may explore painful feelings, emotions and experiences. Besides, they may feel emotionally uncomfortable at times. They may cry, get upset or feel angry during a challenging session, or may also feel physically drained. However, the therapists will minimize any risks. The coping skills patients learn can help to manage and conquer negative feelings and fears.

The results of this study may provide some insights that may lead to better care for patients with recent onset chronic knee pain to enhance in managing pain. It may heightened the potential importance of cognitive behavioral intervention aiming to reduce levels of pain, functional disability, depressive and anxiety severity symptoms, pain catastrophising, fear- avoidance beliefs and increase levels of pain self- efficacy in the management of chronic knee pain patients. The study described in this study will determine comparative efficacy of these programs and the results will assist healthcare providers who are involved in the delivery of non- pharmacological interventions, researchers in the field of osteoarthritis, officials in healthcare governance and policy makers in planning for future arthritis self- management strategies, in order to effectively reduce health and economic burden of knee osteoarthritis.

## **1.3 RESEARCH OBJECTIVES**

The General objective of this study is:

To develop and implement a cognitive behavioral therapy module, and to evaluate its effectiveness in reducing level of knee pain, functional disability, psychological distress (depression, anxiety and stress), pain catastrophising, fear- avoidance beliefs, and improving in self- efficacy in pain management in patients with pain and dysfunction due to osteoarthritis of the knee.

The Specific objectives include:

1. To determine the socio- demography (*age, gender, ethnicity, income, occupation, education Level, type of cohabitation, marital status*) and patients' clinical characteristics (*duration of symptomatic knee OA, comorbidity,*

*treatment, knee affected, knee radiography*), level of knee pain and functional disability, depression, anxiety, fear- avoidance beliefs, pain catastrophising and self- efficacy in pain management level amongst patients with knee osteoarthritis.

2. To develop and implement a cognitive behavioral therapy module in patients with osteoarthritis of the knee.
3. To evaluate the effectiveness of a cognitive behavioral therapy module in reducing knee pain intensity, functional disability, psychological distress (depression, anxiety and stress), fear- avoidance beliefs and pain catastrophising level among knee osteoarthritis patients.
4. To evaluate the effectiveness of a cognitive behavioral therapy module in improving in self- efficacy in pain management level among knee osteoarthritis patients.

#### **1.4 RESEARCH HYPOTHESIS**

**H1:** There is no significant difference between the sociodemographic characteristics of patients enrolled at Orthopaedic Clinic in Hospital Serdang and Hospital Putrajaya

**H2:** The cognitive behavioral therapy module is effective in reducing knee pain intensity in patients with osteoarthritis of the knee.

**H3:** The cognitive behavioral therapy module is effective in reducing functional disability in patients with osteoarthritis of the knee.

**H4:** The cognitive behavioral therapy module is effective in reducing depression in patients with osteoarthritis of the knee.

**H5:** The cognitive behavioral therapy module is effective in reducing anxiety in patients with osteoarthritis of the knee.

[figure not shown]
**H6:** The cognitive behavioral therapy module is effective in reducing stress in patients with osteoarthritis of the knee.

**H7:** The cognitive behavioral therapy module is effective in reducing fear- avoidance beliefs in patients with osteoarthritis of the knee.

**H8:** The cognitive behavioral therapy module is effective in reducing pain catastrophising in patients with osteoarthritis of the knee.

**H9:** The cognitive behavioral therapy module is effective in improving self- efficacy in pain management in patients with osteoarthritis of the knee.

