### 3.5 SAMPLE SIZE ESTIMATION

The formula for calculating sample size in hypothesis testing by comparing means will be used (Lameshow et al., 1990):

$$n = \frac{2\bar{\delta}^2[Z_{1-\alpha/2} + Z_{1-\beta}]^2}{(\mu_1 - \mu_2)^2} \quad (\text{For continuous variable})$$

Where:

(a) Using an assumed expected outcome of **knee pain intensity decrease** within 6 months of therapy,

$\bar{\delta}$  = estimated standard deviation (assumed to be equal for each group) is 10.85 (Wideman et al., 2014)

$\mu_1$  = estimated mean knee pain score for at least 6 months is 16.54

$\mu_2$  = estimated mean baseline knee pain score is 20.68 (Wideman et al., 2014)

$Z_{1-\alpha/2}$  = standard error when  $\alpha = 0.05$  (95% Confidence Interval) = 1.96

$Z_{1-\beta}$  = standard error associated with power = 0.842 ( $\beta = 0.20$ )

Power ( $1-\beta$ ) = 80%

Effect size ( $ES\mu$ ) =  $\mu_1 - \mu_2 / \bar{\delta}$  where  $\bar{\delta}$  = pooled standard deviation =  $\sqrt{\delta_1 + \delta_2} / 2$

$ES\mu = 0.38$  which corresponds to  $n = 109$

Based on the above formula, the required minimum sample size for each group,  $n$  is **109**. To factor in 20% attrition, total required per group will be **131**; hence a total of **262** patients will be required for the sample in both groups.

(b) Using an assumed expected outcome of **functional disability decrease** within 6 months of therapy,

$\bar{\delta}$  = estimated standard deviation (assumed to be equal for each group) is 35.61 (Wideman et al., 2014)

$\mu_1$  = estimated mean functional disability score for at least 6 months is 59.50

$\mu_2$  = estimated mean baseline functional disability score is 74.38 (Wideman et al., 2014)

$Z_{1-\alpha/2}$  = standard error when  $\alpha = 0.05$  (95% Confidence Interval) = 1.96

$Z_{1-\beta}$  = standard error associated with power = 0.842 ( $\beta = 0.20$ )

Power ( $1-\beta$ ) = 80%

Effect size ( $ES\mu$ ) =  $\mu_1 - \mu_2 / \bar{\delta}$  where  $\bar{\delta}$  = pooled standard deviation =  $\sqrt{\delta_1 + \delta_2} / 2$

$ES\mu = 0.42$  which corresponds to  $n = 90$

Based on the above formula, the required minimum sample size for each group, n is **90**. To factor in 20% attrition, total required per group will be **108**; hence a total of **216** patients will be required for the sample in both groups.

(c) Using an assumed expected outcome of **depression level decrease** within 6 months of therapy,

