### **3.13 DATA ANALYSIS PLAN**

Data collected will be analyzed using Statistical Package for Social Sciences software (SPSS) version 21. Parametric tests (T-test, repeated measures ANOVA and correlation analysis) will be performed. P value for test of significance of results will be set at 0.05, alpha level (Type 1 error) at 0.05 (Confidence Interval of 95%). Analysis of outcomes will be by intention-to-treat where all participants who were randomized and entered the trial need to be included in the analysis in the condition to which they were assigned, regardless of whether they completed the trial, or may even have switched over to receive the incorrect treatment, per-protocol (complete case) analysis and chi square test.

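### H1 in section 1.4 is a no-difference statement about the two hospitals that the stated methods could support only through p > 0.05, which does not show similarity (minor)

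*Protocol*

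**What the plan says.** Protocol 1.4 sets out nine research hypotheses. The first reads "There is no significant difference between the sociodemographic characteristics of patients enrolled at Orthopaedic Clinic in Hospital Serdang and Hospital Putrajaya". The other eight claim an effect of the module; H2, for instance, reads "The cognitive behavioral therapy module is effective in reducing knee pain intensity in patients with osteoarthritis of the knee".

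Specific objective 1 in 1.3 asks for socio-demographic characteristics to be determined and lists eight: "age, gender, ethnicity, income, occupation, education Level, type of cohabitation, marital status". It asks for no comparison between hospitals.

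The methods are in 3.13: "Parametric tests (T-test, repeated measures ANOVA and correlation analysis) will be performed", with the further mention of "per-protocol (complete case) analysis and chi square test". The threshold is given as "P value for test of significance of results will be set at 0.05, alpha level (Type 1 error) at 0.05". No equivalence margin, equivalence test or confidence-interval criterion for similarity appears in the protocol.

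Section 3.5 derives the sample size from changes in outcome scores only. The number of patients to come from each hospital is not stated.

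**The concern.** A difference test can give evidence against equality. Failing to reject does not give evidence for it, unless the test was sensitive enough to find any difference that matters. H1 predicts non-significance, and the only tools offered are difference tests at 0.05. Its sole route to support is therefore p > 0.05, and the smaller or more uneven the hospital samples, the easier that is to obtain.

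The rule could also work poorly when H1 is true. H1 covers a whole set of characteristics. If each were tested at 0.05 and any one significant result counted against H1, chance alone would often reject it.

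At stake is the soundness of the answer reported for one numbered hypothesis. The treatment effect is not at stake.

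**Working it through.** **Inputs from the protocol.** Two-sided 0.05 (3.13; in 3.5, "95% Confidence Interval) = 1.96"). Planned total 262, or 300 names drawn for allocation (3.8). Eight socio-demographic characteristics (1.3).

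**Assumed inputs.** Hospital split: 131/131 or 52/210 (about 20:80). True hospital differences: 0.2, 0.3 and 0.5 SD for a continuous characteristic, and 60% v 75% for a binary one. The protocol gives none of these.

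**1. The plan's own sample size.** There is no figure for H1. For knee pain, n = 2 × 10.85² × (1.96 + 0.842)² / (20.68 − 16.54)² = 107.85. With the effect size rounded to 0.38, n = 2 × (2.802/0.38)² = 108.74, which gives the stated 109. Then 109 × 1.2 = 130.8, so 131 per arm and 262 in all. That size was chosen for the arms and not for the hospitals. Socio-demographic data are collected at baseline, so all 262 are taken as available.

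**2. Chance of missing a true hospital difference, continuous characteristic.** SE in SD units = √(1/n₁ + 1/n₂); missed = 1 − Φ(d/SE − 1.96).

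| Split | SE | 0.2 SD missed | 0.3 SD missed | 0.5 SD missed |
|---|---|---|---|---|
| 131/131 | 0.1236 | 63% | 32% | 2% |
| 52/210 | 0.1549 | 75% | 51% | 10% |

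For example, 0.3/0.1236 = 2.428; 2.428 − 1.96 = 0.468; Φ = 0.68; missed 32%. At 52/210, 0.3/0.1549 = 1.937; 1.937 − 1.96 = −0.023; Φ = 0.49; missed 51%.

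**3. Binary characteristic, 60% v 75%.** With p̄ the pooled proportion, √λ = 0.15 / √[p̄(1 − p̄)(1/n₁ + 1/n₂)]; missed = 1 − Φ(√λ − 1.96).

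- 131/131: p̄ = 0.675, √λ = 0.15/0.0579 = 2.59, missed 26%.
- 52/210 with 60% in the smaller hospital: p̄ = 0.720, √λ = 0.15/0.0695 = 2.16, missed 42%.
- 52/210 with 75% in the smaller hospital: p̄ = 0.630, √λ = 0.15/0.0748 = 2.01, missed 48%.

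**4. With 300 patients.** Power for 0.3 SD is 74% at an even split and 55% at 20:80, so 26% and 45% are missed. The picture is much the same.

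**5. The other direction: hospitals truly alike.** With eight independent tests at 0.05 and an any-one-rejects rule, P(at least one significant) = 1 − 0.95⁸ = 0.337. In a simulation with five of the eight test statistics correlated at 0.3, 0.5 and 0.7, this falls to 32%, 30% and 27%.

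**6. Could the trial show similarity properly?** Take two one-sided tests at 0.05, a true difference of zero, 80% power and an assumed margin m in SD units. Then n per hospital = 2 × [(1.645 + 1.282)/m]². For m = 0.20 this is 429 per hospital; for m = 0.30 it is 191. With 262 in total, split evenly, power would be 0% and 57%. A tight equivalence claim is out of reach at the planned size.

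**The case against.** The strongest reply is that nothing in the trial rests on H1. No objective asks for a hospital comparison. The primary and secondary outcomes (3.9), the sample size (3.5) and the analysis (3.13) do not use it, and no section makes pooling the hospitals or choosing a model conditional on it. This stands, and it is why the point is minor.

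Three stronger readings are tempting and are not supported.

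- A reader might infer that the trial will report the hospitals as equal, or treat them as interchangeable. The protocol does not say how H1 will be concluded. H1 may be a conventional null placed in the wrong list, and 3.15 cites the restriction to two hospitals only as a limit on generalisability.
- A reader might infer that H1 is meant to vouch for balance between the CBT and control arms. It names only hospitals; for the arms the protocol relies on randomisation (3.1, 3.8).
- A reader might take the one-third false-rejection rate as a property of the plan. Section 3.13 assigns no test to H1 and states no any-one-rejects rule. A statistical analysis plan, if one exists, may settle how such comparisons are tested and combined. The list itself also varies: 3.9 drops occupation and adds distance to hospital.

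The miss rates rest on assumed gaps and splits, and modest power for modest differences would affect most site tables of this size. What remains is the wording: a hypothesis stated in terms of non-significance, with only difference tests to judge it.

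**Conclusion.** The point holds as a minor one. As written, H1 could be supported only by p > 0.05, and that does not show that the two hospitals' patients are similar. Moderate differences would often be missed: at 262 patients, about 32% to 51% of the time for 0.3 SD, and 26% to 42% for 60% v 75% (48% if the higher proportion lies in the smaller of two very unequal hospitals). Large differences would mostly be found, with 0.5 SD missed 2% to 10% of the time. All these figures depend on assumed gaps and hospital splits.

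The false-rejection figure of about 34% holds only for independent tests under an any-one-rejects rule that the protocol does not state; 27% to 32% is plausible with correlated characteristics. No treatment estimate, error rate for the treatment comparison or sample size changes.

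**What to change.** Delete H1 from the tested hypotheses in 1.4. Under specific objective 1, describe the socio-demographic characteristics by hospital, with estimated differences and 95% confidence intervals. Add a sentence to 3.13 saying that a p-value above 0.05 will not be read as showing that the hospitals' patients are similar.

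The cost is a wording change in 1.4 and a short addition to 3.13, with no new data and no more patients. The one downside is that there is one fewer hypothesis to report as supported. Keeping H1 as a formal similarity claim would need a pre-specified margin and an equivalence test, which the planned size cannot support for tight margins.
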